## 5.2 Exclusion Criteria

1. Diabetes mellitus with any of the following:
  - a. Newly diagnosed within 12 weeks of screening
  - b. HbA1c  $\geq 9.0\%$  at Screening
  - c. Recent change in anti-diabetic pharmacotherapy (change in dosage or addition of new medication within 12 weeks of screening [with the exception of  $\pm 10$  units of insulin])
  - d. Current use of GLP-1 agonists
2. Active pancreatitis within 2 weeks prior to screening
3. History within 6 months of screening of acute or unstable cardiac ischemia (myocardial infarction, acute coronary syndrome, new onset angina, stroke, transient ischemic attack or unstable congestive cardiac failure requiring a change in medication) or major surgery within 3 months of screening
4. Any of the following laboratory values at Screening
  - a. Hepatic:
    - Total bilirubin  $>$  upper limit of normal (ULN), unless prior diagnosis and documentation of Gilbert's syndrome in which case total bilirubin must be  $\leq 3$  mg/dL
      - ALT  $> 2.0 \times$  ULN
      - AST  $> 2.0 \times$  ULN
  - b. Renal:

- Positive test (including trace) for blood on urinalysis. In the event of a positive test, eligibility may be confirmed with urine microscopy showing  $\leq 5$  red blood cells per high power field
- Urine protein/creatinine ratio (UPCR)  $\geq 0.25$  mg/mg. In the event of a UPCR above this threshold, eligibility may be confirmed by a quantitative total urine protein measurement of  $< 300$  mg/24-hr
- Estimated creatinine clearance calculated according to the formula of Cockcroft and Gault  $< 60$  mL/min (CKD-EPI formula can be used instead of Cockcroft-Gault for estimation of GFR in patients with low body weight after discussion with Sponsor Medical Monitor)

- c. Platelet count  $< 140,000$  mm^3
- d. Any other laboratory abnormalities which, in the opinion of the Investigator or the Sponsor, would make the patient unsuitable for inclusion

5. Uncontrolled hypertension (systolic  $> 160$  or diastolic  $> 100$  mm Hg)
6. History of bleeding diathesis or coagulopathy or clinically-significant abnormality in coagulation parameters at Screening
7. History of heart failure with NYHA greater than Class II
8. Active infection requiring systemic antiviral or antimicrobial therapy that will not be completed prior to Study Day 1
9. Known history of or positive test for human immunodeficiency virus (HIV), hepatitis C or chronic hepatitis B
10. Malignancy within 5 years, except for basal or squamous cell carcinoma of the skin or carcinoma *in situ* of the cervix that has been successfully treated
11. Treatment with another investigational drug, biological agent, or device within 1-month of screening, or 5 half-lives of investigational agent, whichever is longer
12. Unwilling to comply with lifestyle requirements ([Section 6.3](#))
13. Use of any of the following:
  - a. Statins, omega-3 fatty acids (prescription or OTC), or fibrates unless on a stable dose for at least 3 months prior to screening and dose and regimen expected to remain constant during the treatment period. Patients taking OTC omega-3 fatty acids should make every effort to remain on the same brand throughout the study.
  - b. Nicotinic acid or derivatives of nicotinic acid within 4 weeks prior to screening
  - c. Systemic corticosteroids or anabolic steroids within 6 weeks prior to screening unless approved by the Sponsor Medical Monitor
  - d. Atypical antipsychotic medications (e.g., olanzapine and clozapine) unless on a stable dose for at least 3 months prior to screening and dose and regimen expected to remain stable throughout the study
  - e. Antihypertensive medication unless on a stable dose for at least 4 weeks prior to screening and dose and regimen expected to remain constant during the treatment period

- f. Glybera gene therapy within 2 years prior to screening
- g. Oral anticoagulants (e.g., warfarin, dabigatran, rivaroxaban, and apixaban) unless on a stable dose for at least 4 weeks prior to screening and regular clinical monitoring is performed
- h. Tamoxifen, estrogens or progestins unless on a stable dose for at least 4 months prior to screening and dose and regimen expected to remain constant during the treatment period
- i. Plasma apheresis within 4 weeks prior to screening or planned during the study
- j. Prior exposure to AKCEA-ANGPTL3-LRX
- k. Any other medication unless stable at least 4 weeks prior to screening (Occasional or intermittent use of over-the-counter medications will be allowed at Investigator's discretion)

14. Blood donation of 50 to 499 mL within 30 days of screening or of > 499 mL within 60 days of screening

15. Known hypersensitivity to any of the excipients of the Study Drug

16. Have any other conditions, which, in the opinion of the Investigator or the Sponsor would make the patient unsuitable for inclusion, or could interfere with the patient participating in or completing the study

## **6. STUDY PROCEDURES**

### **6.1 Study Schedule**

The study will consist of a Screening period, a Treatment period and a Post-treatment period. These periods are described below.

All required study procedures are outlined in [Appendix A](#).

#### ***6.1.1 Screening***

Written informed consent for the study will be obtained prior to the performance of any study-related procedures including screening procedures. An up to 8-week period is provided for completing screening assessments and determining subject eligibility for the study. Subjects on stable diet known to the investigator and followed at the site may skip the 6-week diet run-in. Safety labs may be re-tested for determination of subject eligibility after consultation with the Sponsor Medical Monitor.

During the screening period, subjects will undergo a medical history and physical examination including vital signs, 12-lead ECG, and have blood and urine samples taken for clinical laboratory testing. Subjects will be screened for HIV, hepatitis B, and hepatitis C.

Eligible subjects will be on a stable low-fat diet (according to local clinical guidelines) beginning at least 6 weeks prior to the first dose of Study Drug. The diet stabilization period may be reduced if the patient is following a stable low fat diet for optimal disease control and disease management prior to screening.

Subjects meeting eligibility criteria at Screening will receive standardized meals in preparation for the pre-dose postprandial analysis to be performed on Day -1.

### **6.1.2 Treatment Period**

Subjects will be managed on an outpatient basis. Safety and clinical laboratory evaluations as well as blood sampling for PK analysis will be performed periodically throughout the treatment period. Any AEs and concomitant medications will be recorded.

*Postprandial Assessment (Appendix E):* Postprandial assessments will be performed at Day -1 and at Week 14. Subjects will consume standardized pre-cooked meals (lunches and dinners (provided) and instructions for breakfasts and snacks) for the 2 days prior to the post-prandial evaluations. Patients will remain fasted after consuming the standardized pre-cooked meal for the dinner on the evening prior to their visit. Alcohol consumption is not allowed for the 2 days prior to the post-prandial evaluations. On each of the post-prandial evaluation days, following the first blood draw, patients will consume a standardized liquid meal (which represents about a third of the daily caloric requirements) containing a radioisotope tracer, followed by an 9 hour infusion of two stable isotope tracers and serial blood sampling. Patients will receive a standardized pre-cooked meal 9 hrs after consuming the liquid meal, after which they will fast until the 24 hour blood draw the following day.

### **6.1.4 Post-Treatment Period**

Each subject will be followed for safety assessments for up to 13 weeks after the last dose of Study Drug. During the post-treatment evaluation period, subjects will return to the Study Center for outpatient visits on Days 119, 147 and 182 for safety and clinical laboratory evaluations. A  $\pm$  3-day excursion from the scheduled visit date is permitted for this time period.

## **6.2 Study/Laboratory Assessments**

Laboratory analyte samples will be collected throughout the Study. A list of these analytes is contained in [Appendix B](#). Blood chemistry and urine samples (excluding 24-hour urine collection) should be taken after fasting for approximately 10 hours. During this time subjects can drink water and should ensure that they consume sufficient water to not become dehydrated.

## **6.3 Restriction on the Lifestyle of Subjects**

### **6.3.1 Contraception Requirements**

All male subjects and women of childbearing potential must refrain from sperm/egg donation and either be abstinent† or practice effective contraception from the time of signing the informed consent form until at least a period of 13 weeks after their last dose of study treatment.

Male subjects engaged in sexual relations with a female of child-bearing potential must also encourage their female partner to use effective contraception from the time of signing the informed consent until a period of 13 weeks after the subject's last dose of study treatment.

For the purposes of this study, women of childbearing potential are defined as any female who has experienced menarche, and who does not meet one of the following conditions:

- Postmenopausal: 12 months of spontaneous amenorrhea in females  $> 55$  years of age or, in females  $\leq 55$  years, 12 months of spontaneous amenorrhea without an alternative medical cause and FSH levels in the postmenopausal range for the laboratory involved
- 6 weeks after surgical bilateral oophorectomy with or without hysterectomy
- Post hysterectomy

For the purposes of the study, effective contraception is defined as follows:

For male subjects:

- Effective male contraception includes a vasectomy with negative semen analysis at follow-up, or the use of condoms together with spermicidal foam/gel/film/cream/suppository
- Male subjects with partners that are pregnant must use condoms as contraception to ensure that the fetus is not exposed to the Study Drug

For female subjects and female partners of male subjects:

- Using 1 or more of the following acceptable methods of contraception: surgical sterilization (e.g., bilateral tubal ligation), hormonal contraception, intrauterine contraception/device, or any 2 barrier methods (a combination of male or female condom\* with diaphragm, sponge, or cervical cap) together with spermicidal foam/gel/film/cream/suppository

**†Note:** Abstinence is only acceptable as true abstinence, i.e., when this is in line with the preferred and usual lifestyle of the patient. Periodic abstinence (e.g., calendar, ovulation, symptothermal, post-ovulation methods), declaration of abstinence for the duration of a trial and withdrawal are not acceptable methods of contraception.

**\*Note:** A female condom and a male condom should not be used together as friction between the two can result in either or both products failing.

### 6.3.2 *Other Requirements*

All subjects will be required to fast for approximately 10 hours before visits requiring fasted blood sampling.

## 7. STUDY DRUG

### 7.1 Study Drug Description

#### 7.1.1 *AKCEA-ANGPTL3-LRX (ISIS 703802)*

Study Drug characteristics are listed in [Table 1](#).

A solution of Study Drug contained in stoppered glass vials will be provided. The Study Drug and its storage and preparation instructions will be provided by the Sponsor or designee. The Study Drug must be stored securely at 2° to 8° Celsius and be protected from light.

**Table 1** *Study Drug Characteristics*

Study Drug	AKCEA-ANGPTL3-LRX (ISIS 703802)
Strength	100 mg/ mL
Volume/Formulation	0.8 mL/vial
Route of Administration	SC*

\* SC = subcutaneous

**7.2 Packaging and Labeling**

The Sponsor will provide the Investigator with packaged Study Drug labeled in accordance with specific country regulatory requirements.

**7.3 Study Drug Accountability**

The study staff is required to document the receipt, dispensing, and return of Study Drug supplies provided by the Sponsor. The Study Center must return all used and unused Study Drug to the Sponsor or designee.

**8. TREATMENT OF SUBJECTS****8.1 Study Drug Administration**

Vials are for single use only. Study staff will administer the first dose of Study Drug. Doses will be administered by SC injection, patients or their caregivers may self-administer the study drug following the training given by the study center staff.

Volumes to be administered are shown in [Table 2](#). Please refer to the Study Drug Manual provided by the Sponsor or designee for more detailed instructions for Study Drug preparation and/or administration.

**Table 2 Study Drug Dosing Information**

Volume to Administer	Total Dose
0.20 mL	20 mg (open label)

**8.2 Other Protocol-Required Drugs**

There are no other protocol-required drugs.

Subjects will continue their stable lipid-lowering therapy through the end of the post-treatment evaluation period.

**8.3 Other Protocol-Required Treatment Procedures**

There are no other protocol-required treatment procedures other than those outlined in the schedule of procedures.

**8.4 Treatment Precautions**

No specific treatment precautions are required.

**8.5 Safety Monitoring Rules**

Please refer also to the Guidance for Investigator section of the Investigator's Brochure.

For the purposes of safety monitoring Baseline is defined as the average of the pre-dose test closest to Day 1 and Day 1.

In addition to the standard monitoring of clinical safety parameters, the following guidelines are provided for the monitoring of selected parameters chosen based on preclinical and clinical observations.

In case of discrepancy between the test results from 2 sources, safety-mandated action must be initiated based on the more critical (lower or higher, as relevant) of the 2 values.

Confirmation Guidance: At any time during the Study (Treatment or Post-Treatment Periods), the initial clinical laboratory results meeting the safety monitoring criteria presented below **must be confirmed** by performing measurements (ideally in the same laboratory that performed the initial measurement) on new specimens prior to administering the next dose of Study Drug. All new specimen collections should take place as soon as possible (ideally within 3 days of the initial collection).

Stopping Rule Guidance: The Investigator may interrupt or permanently discontinue study treatment for any safety reason including clinically meaningful changes in clinical laboratory results. The medical monitor should be informed.

Re-dosing Guidance: Subjects with initial laboratory test values that reach a stopping rule must not be re-dosed until the re-test results are available. In general, subjects who do not meet the stopping rules based upon retest may continue dosing. However, the Investigator and the Sponsor Medical Monitor (or appropriately qualified designee) should confer as to whether additional close monitoring of the subject is appropriate. If any of the stopping criteria described in [Section 8.6](#) are met, the subject will be permanently discontinued from further treatment with Study Drug, evaluated fully as outlined below and in consultation with the Sponsor Medical Monitor or appropriately qualified designee, and will be entered into the post-treatment evaluation portion of the study.

Additional Guidance: If possible, a PK sample should be collected as soon as possible after an SAE has occurred (preferably within 2 weeks). In addition, if a patient is asked to return to the clinic for additional evaluations due to an AE, then a PK sample should be taken at the time of the unscheduled visit.

### ***8.5.1 Safety Monitoring Rules for Liver Chemistry Tests***

The following rules are adapted from the FDA guidance for industry, “Drug-Induced Liver Injury: Premarketing Clinical Evaluation,” issued by the U.S. Department of Health and Human Services, Food and Drug Administration, July 2009. For a definition of Baseline, please refer to guidance in [Section 8.5](#) above.

All patients will have liver chemistry tests monitored every 2 weeks during the treatment and follow-up Period.

- In the event of appearance of symptoms or signs of hepatic injury (jaundice, fatigue, nausea, vomiting, right upper quadrant pain or tenderness, fever, rash, abnormal bleeding or bruising, or eosinophilia > ULN) liver enzymes and bilirubin should be tested as soon as possible. Testing at a lab that is local to the patient is permissible for this purpose.
- In the event of an ALT or AST measurement that is > 3 x ULN (or the greater of 2 x baseline value or 3 x ULN if the baseline value was > ULN) at any time during the study (treatment or post-treatment period), the initial measurement(s) should be confirmed as described in [Section 8.5](#).
- Patients with confirmed ALT or AST levels > 3 x ULN should have their liver chemistry tests (ALT, AST, ALP, international normalized ratio [INR] and total bilirubin) retested at least once weekly until ALT and AST levels become  $\leq 1.2 \times$  ULN.

- All results of liver function tests must be reviewed promptly (within 48 hours of receipt) by the Investigator or the designee to ensure that the result has not met the stopping rules per [Section 8.6.1](#). Further Investigation into Liver Chemistry Elevations: For patients with confirmed ALT or AST levels  $> 3 \times$  ULN, the following evaluations should be performed:
  1. Obtain a more detailed history of symptoms and prior and concurrent diseases
  2. Obtain further history for concomitant drug use (including nonprescription medications, herbal and dietary supplement preparations), alcohol use, recreational drug use, and special diets
  3. Obtain a history for exposure to environmental chemical agents and travel
  4. Serology for viral hepatitis (hepatitis A virus [HAV] immunoglobulin M [IgM], hepatitis B surface antigen [HBsAg], hepatitis C virus [HCV] antibody, Cytomegalovirus [CMV] IgM, and EBV antibody panel)
  5. Serology for autoimmune hepatitis (e.g., antinuclear antibody [ANA])

Additional liver evaluations, including gastroenterology/hepatology consultations, hepatic CT or MRI scans, may be performed at the discretion of the Investigator, in consultation with the Sponsor Medical Monitor. Repetition of the above evaluations should be considered if a patient's ALT and/or AST levels reach  $5 \times$  ULN.

All routine liver function test results will be reviewed on an ongoing basis at the weekly safety review by the Medical Monitor.

All lab alerts for abnormal liver function tests must be promptly (within 48 hours of receipt) reviewed by the Investigator and Medical Monitors.

Lab alerts for abnormal liver chemistry tests will be issued for:

1. ALT or AST  $> 3 \times$  ULN;
2. ALT or AST  $> 2 \times$  baseline;
3. total bilirubin  $>$  ULN;
4. ALP  $>$  ULN.

These alert levels are set to anticipate the risk of a combined elevation of aminotransferases and bilirubin as per the FDA Guidance referenced in [Section 8.5.1](#). A more frequent liver function test monitoring may be recommended by the Investigator if warranted. The Investigator should inform the Medical Monitor.

All clinically significant lab alerts for monitoring/ stopping rules as described above are reviewed promptly by the Medical Monitor and communicated with the Investigator and/or the study personnel within 24 hours of receiving an actionable lab alert.

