### ***8.5.2 Safety Monitoring for Renal Function***

All patients will have renal function tests monitored every 4 weeks throughout the study.

In the event of appearance of symptoms or signs consistent with renal dysfunction such as hematuria, polyuria, anuria, flank pain, new-onset hypertension, nausea and/or anorexia, renal function should be tested as soon as possible.

During the course of the study, urinary surveillance will include urinalysis to include urine albumin/creatinine ratio (UACR), urine protein/creatinine ratio (UPCR) and urinary red blood cells (RBCs), as well as serum creatinine and cystatin-C to estimate glomerular filtration rate (eGFR), which will be monitored every 4 weeks.

All renal function test results will be reviewed on an ongoing basis at the safety review by the Medical Monitor.

All results of renal function tests must be reviewed promptly (within 48 hours of receipt) by the Investigator or the designee to ensure that the result has not met the stopping rules per [Section 8.6.2](#).

Lab alerts for abnormal renal tests will be issued for:

- Creatinine clearance (by CKD-EPI formula) decrease from baseline > 25%,
- Urine albumin/creatinine ratio (UACR) > 250 mg/g, urine protein/creatinine ratio (UPCR) > 0.5 mg/mg, or
- An increase in serum creatinine from baseline > 0.3 mg/dL).

These alert levels are set to anticipate and prevent the risk of a medically significant change in renal function while receiving Study Drug.

In the event of a confirmed (as described in [Section 8.5](#)) laboratory result meeting one or more of the above criteria, dosing with the Study Drug should be interrupted and the Study Medical Monitor informed.

In addition, the following supplemental renal tests should be immediately obtained:

- Serum creatinine,
- Urine culture,
- 24-hour urine sample for creatinine clearance,
- Urine albumin and urine protein,
- Urine microscopy sample with inspection of sediment.

The Investigator should also review the patient's concomitant medications for potentially nephrotoxic agents, and, with the results of these evaluations, review any decision to continue or discontinue the patient in consultation with the Study Medical Monitor.

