## **10. STATISTICAL CONSIDERATIONS**

### **10.1 Study Endpoints, Subsets, and Covariates**

For fasting lipid measurements, the values for the Month 3 analysis time point are defined as the average of Week 13 (Day 85) and Week 14 (Day 92) fasting assessments.

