## **14. APPENDICES**

## **Appendix A      Schedule of Procedures**

## Appendix A Schedule of Procedures

Study Period	Screen/ Run-in a	Treatment Period										Post-treatment Follow-up		
		-8 to -1	1	3	5	7	9	11	13	14/ET			18	22
Study Week	-56 To -1	1 b	15	29	43	57	71	85	92	94	95	120	148	176
Visit and Testing Window +/- Days	0	0	2	2	2	2	2	2	2	0	0	3	3	3
Informed Consent	X													
Inclusion/Exclusion Criteria	X	X												
Medical History	X													
Height & Weight c	X	X		X		X			X					X
Vital Signs	X	X		X		X			X			X	X	X
Physical Examination d	X	X		X		X			X					X
12- lead ECG (triplicate)	X	X		X		X			X					X
24-hour urine creatinine clearance and protein	X													
Abdominal Pain Assessment	X	X		X		X			X					X
Urinalysis	X	X		X		X			X			X	X	X
Blood Draw e	Chemistry Panel (+ CPK) f,g	X	X	X	X	X	X	X	X			X		X
	CBC with Differential f,g	X	X	X	X	X	X	X	X			X h	X	X
	Serum Lipid Panel	X	X		X		X		X	X		X	X	X
	PD Panel		X		X		X		X	X		X	X	X
	Coagulation (aPTT, PT, INR)	X	X		X		X			X		X	X	X
	Complement Markers C5A, Bb	X	X							X				
	hsCRP	X	X		X		X			X				X
	Hepatitis B, C, HIV, TSH, Free T 4	X												
	Plasma PK i		X 		X 	X 	X 	X 		X		X	X	X
	Genetic Testing j	X												
	Anti-ANGPTL3-L RX Antibodies		X 		X 		X 			X		X		X
	FSH (women only, if applicable) k	X												
	Serum Pregnancy Test k	X	X		X		X		X	X		X	X	X

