## **Appendix B     List of Laboratory Analytes**

## Appendix B List of Laboratory Analytes

Based on emerging data from this or future studies, additional tests not listed below may be performed on stored samples to better characterize the profile of AKCEA-ANGPTL3-LRX or other similar oligonucleotides.

Clinical Chemistry	Screening Tests	Hematology	Inflammatory
Panel			

 
Sodium
 
Potassium
 
Chloride
 
Bicarbonate
 
Total protein
 
Albumin
 
Calcium
 
Magnesium
 
Phosphorus
 
Glucose
 
Insulin
 
BUN
 
Creatinine
 
Uric Acid
 
Total bilirubin
 
Direct (conjugated) bilirubin
 
Indirect (unconjugated) bilirubin
 
ALT
 
AST
 
Alkaline phosphatase
 
Creatinine kinase
 
Cys-C
 
	
 
Hepatitis B surface antigen
 
Hepatitis C antibody
 
HIV antibody
 
FSH (women only)
 
Serum <math>\beta</math>hCG
 
	
 
Blood viscosity
 
Red blood cells
 
Hemoglobin
 
Hematocrit
 
MCV, MCH, MCHC
 
Platelets count
 
Platelets function
 
White blood cells
 
WBC Differential (% and absolute) 
 
Neutrophils
 
Eosinophils
 
Basophils
 
Lymphocytes
 
Monocytes
 
 
 
	
 
Hs-CRP
 
Cytokine panel 
 
IL-1b,
 
IL-6,
 
IL-8
 
 
 

Fasting Lipid Panel			

 
Total cholesterol
 
Total ApoB
 
ApoB-100
 
ApoB-48
 
LDL cholesterol
 
HDL cholesterol
 
Total Triglycerides
 
CM triglycerides
 
VLDL cholesterol
 
VLDL triglycerides
 
Non-HDL cholesterol
 
	
 
ANGPTL3
 
ANGPTL4
 
ANGPTL8
 
ApoA-I
 
ApoB
 
ApoC-III
 
		
	Specialized Lipoprotein and post-prandial Analyses 	Thyroid Panel	Urinalysis

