## **Appendix C PK Sampling Schedule**

**Appendix C PK Sampling Schedule**

D1	D29	D43	D57	D71	D92	D120	D148	D176
Pre-dose	Pre-dose	Pre-dose	Pre-dose	Pre-dose	Anytime	Anytime	Anytime	Anytime

Note: D = Day

**Appendix D     Grading Scale for Adverse Events Relating to  
Laboratory Abnormalities**

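### After the last dose, Appendix A marks chemistry panels only on Days 120 and 176, although the text requires liver tests every 2 weeks and serum renal tests every 4 weeks

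*Combined protocol and SAP*

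**What the plan says.** All references are to Amendment 1 unless stated otherwise.

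- Section 8.5.1 sets the liver rule: "All patients will have liver chemistry tests monitored every 2 weeks during the treatment and follow-up Period". For a raised ALT or AST it adds that "at any time during the study (treatment or post-treatment period), the initial measurement(s) should be confirmed", so the confirmation rule is meant to work after dosing has ended.
- Section 8.5.2 sets the renal rule: renal function every 4 weeks for the whole study, including "serum creatinine and cystatin-C to estimate glomerular filtration rate (eGFR), which will be monitored every 4 weeks".
- Appendix B puts ALT, AST, bilirubin, alkaline phosphatase, creatinine and cystatin-C in one clinical chemistry panel.
- Section 6.1 sends sites to the schedule table: "All required study procedures are outlined in" Appendix A.
- In Appendix A, the row that begins "Chemistry Panel (+ CPK" is marked at Screening, at every two-week visit from Day 1 to Day 85, and then on Days 120 and 176. Days 92 and 148 are blank.
- Footnote g to that row says who may do the draws and caps the spacing of centre visits during treatment. Footnote h adds 14-day samples for platelets only.

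**The concern.** The text and the table give sites two different follow-up schedules. A site that works from Appendix A, as Section 6.1 invites it to, would leave out tests that Sections 8.5.1 and 8.5.2 require.

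The confirmation rule and the laboratory alerts can act only on a sample that has been drawn. With no chemistry between Days 120 and 176, a change in ALT, bilirubin or creatinine in a patient without symptoms could go unseen for 8 weeks. Section 2.3.4 gives a terminal half-life of 3 to 5 weeks, so exposure does not end with the last dose.

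A second, less certain point concerns patients who stop early. Section 8.8.1 makes the early termination procedures the minimum for those who decline further follow-up, and the Week 14/ET column shows no chemistry panel.

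**Working it through.** **Reading the table.** The amended blood-draw rows come through with 13 cells for 14 day columns, so the alignment has to be checked first. Assume that Days 94 and 95 share one cell. The columns are then Screening, 1, 15, 29, 43, 57, 71, 85, 92, 94/95, 120, 148 and 176.

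- The PK row gives Days 1, 29, 43, 57, 71, 92, 120, 148 and 176, exactly the days in the Appendix C "PK Sampling Schedule".
- The lipid row includes Days 85 and 92. Section 10.1 needs both, because it defines the Month 3 value as "the average of Week 13 (Day 85) and Week 14 (Day 92) fasting assessments".
- The chemistry row gives Screening and Days 1, 15, 29, 43, 57, 71, 85, 120 and 176.
- As an alignment check only, the superseded chemistry row in the original protocol has a full 18 cells for 18 columns. It too has Days 92 and 148 blank and Days 120 and 176 marked.

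**Follow-up length.** The last dose is on Day 1 + 12 × 7 = 85. The final visit is Day 176, so follow-up lasts 176 − 85 = 91 days.

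**Gaps between marked panels.** From Day 1 to Day 85 there are six gaps of 14 days, so the treatment period meets the liver rule. After that, using the Appendix A windows (±2 days at Day 85, ±3 days at Days 120 and 176):

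| Gap | Nominal | Within windows | Relative to 14 days (liver) | Relative to 28 days (renal) |
|---|---|---|---|---|
| Day 85 to 120 | 35 days | 117 − 87 = 30 to 123 − 83 = 40 | 35/14 = 2.5 | 35/28 = 1.25 |
| Day 120 to 176 | 56 days | 173 − 123 = 50 to 179 − 117 = 62 | 56/14 = 4 | 56/28 = 2 |

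**Draws required and draws marked after Day 85, per patient.**

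- Liver at strict 14-day spacing: Days 99, 113, 127, 141, 155 and 169, which is 6 draws. With a closing draw at Day 176 it is 7.
- Renal at strict 28-day spacing: Days 113, 141 and 169, which is 3 draws. With a closing draw it is 4.
- Marked: 2.
- Shortfall: 6 − 2 = 4 or 7 − 2 = 5 liver draws, and 3 − 2 = 1 or 4 − 2 = 2 renal draws. For 3 patients that is 12 or 15 liver draws and 3 or 6 renal draws.

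**If a Day 92 mark was lost.** This is possible, because the neighbouring CBC row was marked on Day 92 in the superseded table and is blank now. The first gap would then run from Day 92 to Day 120, which is 28 days. That is acceptable for renal tests and still twice the liver interval. The 56-day gap does not change.

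**Whether other rows cover the gap.** Urinalysis and coagulation (with INR) are marked on Days 92, 120, 148 and 176. Neither supplies ALT, AST, bilirubin, serum creatinine or cystatin-C.

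**The case against.** The strongest reply is that the table is incomplete rather than the monitoring absent. Section 8.5.1 supplies the interval and footnote g allows home draws. Section 6.1.4 brings patients back on Days 119, 147 and 182 for safety and laboratory evaluation, so an 8-week blind spot needs a site to read Appendix A alone. This has some force. But Section 6.1.4 does not name chemistry, footnote g gives no dates, and Section 6.1 directs sites to that table.

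A second reply is that 4-weekly testing may have been intended. Section 3.4.3 sets follow-up visits every four weeks. Section 8.5.3 also asks for platelets every 2 weeks for the whole study, yet footnote h reduces them to the Week 22 and Week 26 visits after 6 weeks. Amendment 1 did edit the liver sentence in Section 8.5.1, but only to correct a word, so the edit does not show that the interval was reconsidered. This stands as a reason to let the sponsor choose which side to correct. It does not remove the conflict.

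A third reply is that the renal part is small. The first gap exceeds 28 days by 7 days nominally, or by 2 days at the favourable edge of the windows. On existing visit days, the clear omission is the Day 148 serum sample. That is fair, and the closing-draw counts (7 and 4) are a convention, which is why both counts are given.

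The consequence is also limited. For patients who complete treatment, no dosing decision rests on chemistry after Day 85. Retest rules cover patients with symptoms or a known signal, and Section 2.3.4 reports no significant liver or renal changes in Phase 1.

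**Conclusion.** The concern holds. In the current text, Appendix A contradicts both Section 8.5.1 and Section 8.5.2 after the last dose. The nominal gaps of 35 and 56 days exceed both required intervals. The second gap stands however Day 92 is read, and even at its shortest within the windows (50 days) it exceeds the 28-day rule.

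The conclusion rests on the column alignment described above, which Appendix C, Section 10.1 and the superseded full-width row all support. The early-termination point is less secure, because a Day 92 mark may have been lost. It matters only for early stoppers who decline further follow-up; a blank Day 92 in itself breaks no interval rule for completers.

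This is a safety-monitoring inconsistency that should be corrected. Treatment-period chemistry and the triglyceride endpoint are not affected.

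**What to change.** **Mark the chemistry panel on Day 92/ET and Day 148.** Blood is already drawn at both visits. The nominal gaps after Day 85 become 92 − 85 = 7, 120 − 92 = 28, 148 − 120 = 28 and 176 − 148 = 28 days. Within the existing windows the three later gaps range from 22 to 34 days. The renal rule is then met on the nominal visit days, and early stoppers get a closing panel. The cost is 2 panels per patient (6 for 3 patients), with no extra visit or venepuncture.

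**Settle the liver interval one way or the other.**

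1. Keep the 2-week rule and add home-health or centre draws on Days 106, 134 and 162. Every interval from Day 92 to Day 176 is then 14 days. This costs 3 draws per patient (9 for 3 patients), assuming none is shared with platelet sampling.
2. If 4-weekly testing in follow-up was intended, amend the sentence in Section 8.5.1 to say so. This costs one line.

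Option 1 is the sensible default, because it keeps the safety rule as written. The choice is a clinical one for the sponsor, but text and table must end up the same.
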